## **6. MILESTONES**

Milestone	Planned Date
IRB/IEC approval	30 October 2016
Start of data collection	05 April 2017
End of data collection	05 June 2021
Final report of study results:	05 June 2022

## **7. RATIONALE AND BACKGROUND**

### **7.1 DEFINITION**

Idiopathic pulmonary fibrosis (IPF) is defined as a specific form of chronic, progressive fibrosing interstitial pneumonia of unknown cause, occurring primarily in older adults, limited to the lungs [1]. It is characterized by progressive worsening of dyspnea and lung function and is associated with a poor prognosis. As stated in an international consensus statement jointly issued by ATS/ERS, JRS and ALAT, IPF is a distinct clinical entity associated with the histologic and/or radiologic appearance of usual interstitial pneumonia (UIP) [1]. The definition of IPF requires the exclusion of other forms of interstitial pneumonia including other idiopathic interstitial pneumonias (IIP) and interstitial lung disease (ILD) associated with environmental exposure, medication, or systemic disease [1].

IPF predominantly presents in older individuals (cases in persons aged less than 50 years are rare), with a preponderance in men and previous or current smokers. Patients present with unexplained chronic exertional dyspnea, and commonly with cough, bibasilar inspiratory crackles, and finger clubbing.

### **7.2 INCIDENCE AND PREVALENCE**

Overall, epidemiological data on the incidence and prevalence of IPF are limited, as stated in the consensus statement issued by ATS/ERS/JRS/ALAT [1].

In a population-based study from New Mexico, the incidence of IPF was estimated at 10.7 cases per 100,000 per year for men and 7.4 cases per 100,000 per year for women [1]. In the UK, an overall incidence rate of only 4.6 per 100,000 person-years was reported, however, with an estimated increase by 11% annually between 1991 and 2003 (not attributed to aging of the population or increased ascertainment of milder cases) [4]. In the USA, based on a large database of healthcare claims in a health plan, the incidence of IPF was estimated between 6.8 and 16.3 per 100,000 persons [5].

Prevalence estimates for IPF, as assessed in England, Japan, New Mexico, Norway, Italy and Greece, have varied widely from 1,82 to 35,51 cases per 100,000 in the general population [2, 6-9, 26]. The wide range in these numbers is likely explained by the previous lack of uniform definition used in identifying cases of IPF, as well as by differences in study designs and populations [1]. In the USA, a recent analysis based on healthcare claims yielded a prevalence estimate between 4.0 - 42.7 per 100,000 persons depending on the case definition used [5]. Another study from the US, estimated a prevalence of 58.7 per 100,000 (95% CI 56.3-61.2) for IPF, after correction of the estimate for its PPV after chart review [27]. It is unknown if the incidence and prevalence of IPF are influenced by geographic, ethnic, cultural, or racial factors [1]. In Italy, a relevant study from N. Agabiti, M. A. Porretta, L. Bauleo, A. Coppola, et al, conducted at Lazio region, concluded that IPF incidence and prevalence in this large central-southern Italian region are strikingly similar to those derived from the hospital and general medicine databases of northern Europe and the United States. At the same time, this study stated that IPF incidence is more likely driven by industrialization, urbanization and western lifestyles than the ethnic variables characterizing different European regions [25]. In 2016, another study conducted in Lombardy, the most populous region of Italy, estimated the annual incidence and prevalence at 7.5 and 25.6 per

[figure not shown]
100,000 person-years, respectively. This same study indicated that prevalence of IPF increased across the years while incidence remained stable, concluding that survival with IPF has improved. However, Italian trends in incidence and prevalence of IPF are still unknown [26].

### 7.3 DIAGNOSIS

According to the consensus statement jointly issued by ATS/ERS/JRS/ALAT in 2011, the diagnosis of IPF requires the following [1]:

- Exclusion of other known causes of ILD (e.g., domestic and occupational environmental exposures, connective tissue disease, and drug toxicity).
- The presence of a UIP pattern on HRCT in patients not subjected to surgical lung biopsy
- Specific combinations of HRCT and surgical lung biopsy pattern in patients subjected to surgical lung biopsy

Figure 1. Diagnostic algorithm according to ATS/ESC/ERS/JRS/ALAT guidelines [1]

## **7.4 NATURAL COURSE**

Data on the natural course of IPF are from retrospective and a few prospective studies, including the placebo arms of clinical trials (limited to short observation periods and by in/exclusion criteria). The previously reported median survival time of 2-3 years from the time of diagnosis could be an underestimate, at least when accounting for patients with preserved lung function. Notably, the natural course is unpredictable for a given patient at the time of diagnosis, while the majority of patients experience steady worsening (slow progression), others remain stable, or have rapid progression of disease [\[10-11\]](#). Acute respiratory worsening either due to secondary complications (e.g. pneumonia, pulmonary embolism, pneumothorax or cardiac failure) or due to unknown reasons (in this case the term acute exacerbation is used) are suggested to occur in about 5-10% annually [\[1\]](#). A recent retrospective review of 461 patients with IPF has found that the 1- and 3-year incidences of acute exacerbations were 14.2% and 20.7%, respectively [\[12\]](#).

## **7.5 THERAPY**

The ATS/ESR/JRS/ALAT guideline finalized end of 2010 and issued in 2011 stated: “The committee did not find sufficient evidence to support the use of any specific pharmacologic therapy for patients with IPF.” [\[1\]](#)

A number of drugs are used for the treatment of IPF, including steroids, azathioprine and N-acetylcysteine (and sometimes the latter three in combination). However, recently the NHLBI (part of the National Institutes of Health) has stopped the triple- drug therapy arm consisting of prednisone, azathioprine, and N-acetylcysteine (NAC) of the US PANTHER trial due to safety concerns. [\[13\]](#)

The only drug that until recently had received regulatory approval for the treatment of mild or moderate IPF in Europe and Japan was pirfenidone, a pyridone compound with pleiotropic, anti-inflammatory, antifibrotic, and antioxidant properties, with antagonism of TGF- $\beta$ 1 effects [\[14\]](#). On October 2014, FDA approved simultaneously pirfenidone and nintedanib, a tyrosine kinase inhibitor that was researched and developed by Boehringer Ingelheim [\[15\]](#) for IPF treatment. Moreover, on January 15, 2015 EMA approved the use of nintedanib on all IPF stages. According to the updated Guidelines for IPF treatment, released on July of 2015, conditional recommendations have been made for treatment with novel agents such as pirfenidone and nintedanib, as well as antiacid treatment. The treatment of IPF patients should be individualized, according to the patient and the physician should calculate the benefit of using one intervention instead of another [\[2\]](#). New drugs for IPF treatment will also be documented in this registry.

As for supportive pharmacological and non-pharmacological therapy, the evidence is limited, too. This includes anticoagulants, long-term use of oxygen, mechanical ventilation and lung transplantation [\[1\]](#).

## **7.6 ECONOMIC ASPECTS**

IPF is of high interest for the health-care system as well as for payers when considering costs. However, data on economic issues are limited, while needed for assessing cost-effectiveness of interventions [\[16-17\]](#).

The current IPF Registry will be suitable for various cost analyses. All pharmaco- and health economic parameters will be derived from either one or both of the following ways and in most cases subsequently priced:

- Assessment of the direct health resources use
- Indirect health assessment with adjustment of recorded clinical outcomes.

## **7.7 RATIONALE FOR THE PRESENT REGISTRY**

Long-term data on the natural course of IPF are missing. Further, there is lack of information on detailed patient characteristics. While in IPF substantial efforts are being made to investigate the efficacy and safety of new drugs in controlled clinical trials, there is a lack of data on the situation and treatment of patients in everyday clinical practice. In a call for action on an IPF registry by Wilson in 2008, it was noted that improved survival from this disease is dependent on better understanding of the epidemiology of the disease, its diagnostic spectrum and an analysis of outcomes from emerging therapies at a significant level. [\[17\]](#) In Greece, Karakatsani et al, conducted a multicenter research (survey) in 2009, using a one page questionnaire, in order to evaluate the incidence and prevalence of Interstitial Lung Diseases in Greece. The annual incidence of IPF was estimated to be 0.93 cases per 100,000 whereas prevalence was estimated to be 3.38 cases per 100,000. Since then, the diagnostic criteria, the international guidelines [\[1\]](#) the standard medical care and the composition of the population have changed, whereas more studies have been conducted regarding the incidence and prevalence of IPF (please refer to [Section 7.2](#)).

A registry can document the introduction of new treatments and complement data from the controlled randomized trials. The present clinical IPF registry will record standard epidemiological parameters by using a web-based electronic case report form. No additional biobank specimen will be collected (only already existing data will be used from examinations that have been performed according to the routine clinical practice of the physicians). IPF diagnosis will be based upon criteria, defined according to the consensus statement jointly issued by ATS/ERS/JRS/ALAT for the collection of standard practice data, and as it is also described in the inclusion criteria section. Moreover, in the present IPF registry, drug utilization and treatment patterns under clinical practice conditions will be documented in detail. Furthermore, health economic aspects will be investigated.

## **8. RESEARCH QUESTION AND OBJECTIVES**

The overall objective of the present IPF Registry is to gain further insight on the characteristics, management, disease progression and the outcomes of patients with IPF, as diagnosed and treated under real-world, clinical practice conditions in Greece.

More specifically, this registry will be used to:

- Provide a comprehensive clinical picture of IPF
- Track access to health care and cost of caring for IPF patients over time
- Examine the implementation of treatment guidelines [2], used on patients diagnosed with IPF, according to the existing diagnosis guidelines [1]
- Characterization of patients on different treatments

Furthermore, this project aims to provide information regarding survival and mortality causes, IPF exacerbations as well as IPF patient co-morbidities including myocardial infarction, CNS infarction, other arterial thromboembolic events, deep vein thrombosis, hemorrhage, gastrointestinal perforation and pulmonary hypertension (please refer to [Annex 3](#)). In addition, data regarding IPF patient hospitalization will be collected and evaluated with regards to potential respiratory causes, and there will be documentation of treatment patterns and economic aspects. Patients will be followed up for 2 years and information regarding IPF treatment changes since the last visit will be collected.

## **9. RESEARCH METHODS**

### **9.1 STUDY DESIGN**

This IPF registry allows for structured, non-interventional collection of data. A similar protocol was prepared by the [REDACTED] of the [REDACTED] ( [REDACTED] ). This Protocol is based on the main idea of the protocol created by the [REDACTED]. It is a national, multi-center, observational disease and outcomes registry based on new data from a significant sample size of Greek IPF patients. Participating physicians (experts in IPF) will not be subject to any instructions with regard to the diagnosis and therapy of their patients. All examinations performed depend on the discretion and clinical routine of the physician.

The Sponsor of the Study will be [REDACTED] and will own the data and have access to the data. Members of the National Scientific Committee (see title page) will oversee and give scientific advice for the study.

An external Vendor (CRO) will provide the electronic database; the web based eCRF and will perform the statistical analyses and produce the relevant reports according to the Statistical Epidemiological Analysis Plan.

This IPF Registry is not a clinical trial (interventional study) according to the Ministerial Decision No 12/2003 of the Greek Legislation for Clinical Studies, but a non- interventional observation study.

### **9.2 SETTING**

Not applicable

### **9.3 STUDY SITES**

Physicians managing IPF patients are eligible for participation in the study considering their qualifications, their past participation and experience on similar clinical studies and their capacity on recruiting and monitoring patients in the study. In order to ensure adequate patient numbers per center and high quality of data, expert pulmonary centers will be involved. Seven Centers - University Pulmonology Clinics / Reference Centers of Public Hospital Setting have been selected. Eligible patients will be included in a consecutive manner at each site in order to avoid selection bias. It is possible that the number of Sites will increase in order to achieve representation of the entire Greek territory. A minimum of 15 patients per year should be included per center, to ensure that centers have adequate patient numbers to get accustomed to the study procedures. The number of patients per center is defined in the contractual agreement of each Investigator but may be amended in consultation with the Sponsor, thus allowing the inclusion of more patients. Thus, the study will likely be

representative for expert centers in Greece, representing the majority of expert centers in Greece.

### **9.3.1 Study Population**

Eligible for participation in the study patients must fulfill **ALL** the inclusion criteria and **NONE** of the exclusion criteria that are listed below and must be consecutively enrolled:

- Newly diagnosed (less than 6 months) or patients previously diagnosed with IPF (more than 6 months from baseline visit), based upon the consensus statement jointly issued by ATS/ERS/JRS/ALAT in 2011 (see [Annex 6](#) and [Annex 7](#) for HRCT and histological criteria in [Annex 6](#))
  - Exclusion of other known causes of ILD (e.g., domestic and occupational environmental exposures, connective tissue disease, and drug toxicity)
  - Assessment of IPF based on HRCT or combinations of HRCT and surgical lung biopsy, if available
- Age  $\geq 40$  years old at the time of inclusion
- Written informed consent for participation in the registry
- Patients that can be followed up further, during the scheduled study period

None of the following Exclusion Criteria should be fulfilled:

- Expected lung transplantation within the following 6 months
- Participation in clinical trials

Patients will be included in a consecutive manner at each site in order to avoid selection bias. It should be avoided to establish the registries at sites where already other registries are ongoing (if a patient participates in another registry/non - interventional study this needs to be documented and patients need to be analyzed separately).

A subject screening log should be kept at the site, recording basic information (e.g. initials, gender, date of birth, reason for not enrolling the patient etc.) on all patients who were invited to participate in the study, with the information on the eligibility (or reasons for non-eligibility) and date of signed informed consent. In the case of refusal, reasons for refusal should be given. In addition, a log of all patients included into the study (i.e. having given informed consent) will be maintained in the study file at the study site.

### **9.3.2 Withdrawal Criteria**

The patients reserve the right to withdraw consent at any time during the study, without the need for justification and without any impact on their future treatment and care.

Withdrawal of consent means that the patient does not wish or cannot continue to participate in the study any more.

The reasons for withdrawal may include the following:

- Patient or legally accepted representative withdraws informed consent for participation in the study.
- Inclusion or possible participation in any clinical trial, any time within the follow up period of the study, in which the patient has been exposed or is going to be exposed to an investigational product (pharmaceutical product or medical device) or intervention.
- The patient was erroneously included in the registry
- Decision of the investigator/physician
- Important deviation/divergence from the protocol.

The Clinical Monitor at BI or BI's designees must be immediately notified if a patient is discontinued prematurely for any of the instances reasons cited above.

Patients that withdraw from the study should be asked about the reason(s) for withdrawal and the occurrence of adverse events, and should be examined and evaluated by the investigator according to the procedures that are defined in the Final Visit (unless reason for discontinuation is erroneous enrolment of the patient into the study at baseline and unless patient has actively withdrawn consent for any kind of future contacts).

If the patient specifically withdraws consent for future contact about the collection of further information, there will be no such contact whatsoever. However, it is possible to collect information regarding their survival status, if they are publicly available.

The investigators also reserve the right to remove a patient from the study, if according to their clinical judgment this is the necessary for the patient's welfare.

If a patient is removed or withdrawn from the study for any reason, the date, vital status and reason must be documented in the relevant section of the electronic Case Report Form (eCRF).

### **9.3.3      Study Visits**

The registry is scheduled to run for 4 years in total (2 years recruitment + 2 years follow up) (April 2017 to April 2021).

During the follow up period, data will be collected on standard clinical visits which usually are scheduled around: 3-months (+/- 1 month), 6-months (+/- 1 month), 12-months (+/- 2 month), 18-months (+/- 2 month) and 24 months (+/- 2 months), until the end of participation in the study. In case of events, unscheduled visits may be required.

### **9.3.4      Study Discontinuation**

Boehringer Ingelheim reserves the right to discontinue the study overall or at a particular study site at any time for the following reasons:

1. Failure to meet expected enrolment goals overall or at a particular study site
2. Violation of Good Clinical Practice (GCP) (as applicable), the study protocol, or the contract by a study site or investigator, disturbing the appropriate conduct of the study

The investigator / the study site will be reimbursed for reasonable expenses incurred in case of study termination (except in case of the third reason).

## **9.4       VARIABLES**

At baseline, a relevant patient history will be recorded including IPF-related events up to 12 months prior to this visit. The variables to be recorded are listed below as well as in [Annex 4](#):

- Basic (socio-)demographic data including age, gender and race
- Vital Status
- Physical and vital signs examination
- Cardiopulmonary exercise testing (6-minute walk distance and CPET, if performed)
- IPF risk factors (e.g cigarette smoking including pack years, alcohol and substance abuse, environmental and occupational exposure, exposure to drugs associated with IPF, exposure to viral infection possibly related to IPF, gastro-esophageal reflux, genetic factors - family history)
- Co-morbidities.
- Risk of bleeding and thrombosis
- Collection of pre-specified outcome data, only for newly diagnosed patients (such as acute respiratory worsening, exacerbations, hospitalization due to any cause and due to IPF). Please, refer to [Annex 3](#)
- Recording of therapeutic regimens. Assessment of the intensity of treatment, frequencies and resource utilization for pharmaco-economic analyses.
- Methods and procedures used in the diagnosis of IPF and date of diagnosis (HRCT: UIP pattern, possible, inconsistent UIP pattern and not available and SLB: UIP pattern, probable, possible or inconsistent UIP pattern)
- IPF symptoms: Dyspnea, cough, weight loss, fatigue, dizziness, chest pain, anxiety, clubbing, bibasilar crackles
- Autoimmune Biomarker results (No additional specimen will be collected. Only already existing data will be used from exams that have been performed according to the routine clinical practice of the physicians),
- Assessment of function (including lung function, cardiopulmonary exercise testing and/or exercise capacity if available, laboratory values)
- IPF treatment modalities (detailed information on prescribed drugs and dose; previous treatment; start and end dates of previous treatments; non-pharmacological treatment; listing and score for lung transplantation). For the treatments that detailed information will be requested, please refer to [Annex 4](#)

Proprietary confidential information © 2018 Boehringer Ingelheim International GmbH or one or more of its affiliated companies

- Physician's clinical rating of the probable course of IPF (stable, slow or rapid progression)
- Clinical events and hospitalizations especially due to: (acute) respiratory worsening, including pneumonia, exacerbations of IPF, occurrence of pulmonary or cardiovascular complications, pulmonary rehabilitation, pulmonary embolism, pneumothorax, or cardiac failure
- Management of IPF and physician contacts

During follow up visits (prospectively until up to 2 years at least from the inclusion) 3-months (+/- 1 month), 6-months (+/- 1 month), 12-months (+/- 2 month), 18-months (+/- 2 month) and 24 months (+/- 2 months), documentation of events (or last follow up visit) will be carried out. The collection of data will be performed during standard clinical practice visits (i.e. visits should not be performed via telephone contact). In a special event where the physical presence of the patient is not possible, e.g. in case of temporary inability of the patient to visit the expert center, this visit could be performed through telephone contact and this should be recorded in patient's history. Every effort should be made, however, to ensure that the next visit will be performed as planned by the patient in person. If this is not possible the patient will be censored for the rest of the study. Patient will be followed up until death, lung transplantation, consent withdrawal or end of study, whichever comes first and will be censored if one of the events occurs. The following data will be documented:

- Clinical course of IPF (e.g. regarding symptoms, lung functionality, exercise ability, if available)
- Vital status
- Physical and vital signs examination
- Cardiopulmonary exercise testing (6-minute walk distance and CPET, if performed)
- Autoimmune Biomarker results (No additional specimen will be collected. Only already existing data will be used from exams that have been performed according to the routine clinical practice of the physicians)
- Risk of bleeding and thrombosis
- Outcomes of interest (such as acute respiratory worsening, exacerbations, hospitalization due to any cause and due to IPF). Please, refer to [Annex 3](#)
- Recording of therapeutic algorithms (change/complement/interrupt treatment) and non-pharmacological treatment (e.g. start of LTOT, new listing for lung transplantation)
- Physician's clinical rating of the probable course of IPF (stable, slow or rapid

progression)

- Assessment of treatment intensity, frequencies and resource use for pharmacoeconomic analyses for the treatments described under 11.3
- Management of IPF and physician contacts

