## **9.5 DATA SOURCES**

The study will mainly include the recording of new data through a web based system for data collection. Data will be collected by the study doctors as they occur according to standard clinical practice in the approximate visiting schedule indicated above.

Source (primary) patient data related to their medical and IPF history will be collected by the investigators from the patient's medical files/records and will be documented in the relevant eCRF section.

Data regarding treatment modifications, concomitant treatments, study related routine clinical assessments, adverse events (ADRs) and survival status will also be collected. If a patient withdraws early from the study, they will be contacted via telephone at the end of the Study in order to evaluate their survival status. Another follow-up assessment should be performed if possible (unless reason for discontinuation is erroneous enrolment of the patient into the study at baseline), and data should be entered on the eCRF of the next planned visit unless the patient has actively withdrawn consent for any kind of future contacts.

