#### **4. CHANGES IN THE PLANNED ANALYSIS OF THE STUDY**

As described in the study protocol only descriptive analysis will be applied for the purpose of the present study. Further to the summary tables of frequencies and measures of central tendency, Kaplan Meier curves will be produced to illustrate the survival distribution of patients in the study.

Analysis of the baseline characteristics was decided to be performed when all subjects had entered the trial.

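### The in-person visit rule in Protocol 9.4 censors living, reachable patients, conflicts with the next sentence, loses their later events, and may overstate survival unless their deaths are recovered

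*Protocol*

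**What the plan says.** Protocol 9.4 (Variables) sets planned follow-up at months 3, 6, 12, 18 and 24, normally in person. If the patient cannot come, "this visit could be performed through telephone contact". It continues: "Every effort should be made, however, to ensure that the next visit will be performed as planned by the patient in person", and then: "If this is not possible the patient will be censored for the rest of the study". So a telephone visit followed by a second visit that cannot be made in person ends follow-up.

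The next sentence gives a different rule: "Patient will be followed up until death, lung transplantation, consent withdrawal or end of study, whichever comes first". Inability to attend is not on that list.

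Protocol 9.5 adds that if patients withdraw early, "they will be contacted via telephone at the end of the Study in order to evaluate their survival status", with one further follow-up assessment if possible.

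Protocol 8 makes these outcomes an aim: "this project aims to provide information regarding survival and mortality causes, IPF exacerbations". Hospitalization and economic data are listed there too. Protocol 9.8.1 reports follow-up events as incidence rates with 95% confidence intervals. SAP 4 adds that "Kaplan Meier curves will be produced to illustrate the survival distribution of patients in the study". The SAP states no censoring rule for those curves, and SAP 6.6 leaves subjects with an incomplete date of death out of the time-to-event analysis.

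**The concern.** A Kaplan-Meier curve treats a censored patient as having the same future risk as patients of the same follow-up time who remain. Protocol 7.4 describes the disease course: "while the majority of patients experience steady worsening (slow progression), others remain stable, or have rapid progression of disease". A patient who cannot reach the clinic at two planned visits in a row is plausibly further along that course than one who can. Such a patient may still be alive, consenting, reachable by telephone and under the centre's care when follow-up stops.

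Two results are at stake.

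- **Non-fatal outcomes.** Exacerbations, hospitalizations and resource use after censoring are not recorded. Person-time also stops, so an incidence rate is understated only if events are more frequent in the unobserved period. Late in progressive disease that is the likely direction.
- **Survival.** If deaths after censoring are not brought back into the analysis, the curve lies too high.

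**Working it through.** **No figure to reproduce.** Neither document gives an expected survival, dropout or censoring figure for this rule. The size is therefore an illustration.

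**Inputs from the documents.** Visits at months 3, 6, 12, 18 and 24 (Protocol 9.3.3; the 1- and 2-month windows are ignored). Median survival of 2-3 years (Protocol 7.4, which says this may be an underestimate). About 300 patients (Protocol 9.6).

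**Assumptions.** Exponential survival with median m = 24, 30 or 36 months. A share f of patients becomes permanently unable to attend L months before death. No death after censoring is recovered.

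**When the rule bites.** Let D be the time of death. A patient is censored when, for consecutive visits a and b, inability has begun by a (D − L ≤ a) and the patient is alive at b (D > b). This needs L > b − a. The gaps are 3 months (3 to 6) and then 6 months each.

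- L = 3: no pair of visits satisfies the condition, so nobody is censored.
- L = 6: only the pair 3 and 6 can, for deaths with 6 < D ≤ 9.
- L = 12: all pairs can. Together they cover deaths with 6 < D ≤ 24.

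**Deaths missed per 300 patients** = 300 × f × P(D in that interval), with P(D > t) = 0.5^(t/m).

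- m = 24, f = 10%, L = 6: 300 × 0.10 × (0.841 − 0.771) = 2.1.
- m = 24, f = 10%, L = 12: 300 × 0.10 × (0.841 − 0.500) = 10.2.
- m = 36, f = 10%, L = 12: 300 × 0.10 × (0.891 − 0.630) = 7.8.

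A simulation of 400,000 patients per setting gives the same counts.

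**Effect on 24-month Kaplan-Meier survival.** True values are 0.5^(24/m), or 50%, 57% and 63%. Simulated results, as ranges over the three medians with censoring at the second visit:

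| Lead L | f | Overstatement (points) | Deaths missed per 300 |
|---|---|---|---|
| 3 months | any | 0 | 0 |
| 6 months | 10% | 0.4 | 1.5-2.1 |
| 6 months | 25% | 0.9-1.1 | 3.9-5.3 |
| 6 months | 50% | 1.8-2.2 | 7.5-10.4 |
| 12 months | 10% | 2.1-2.4 | 7.8-10.2 |
| 12 months | 25% | 5.3-6.3 | 19.4-25.5 |
| 12 months | 50% | 11.5-13.9 | 39.3-51.3 |

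Censoring at the telephone visit instead gives similar or slightly smaller values.

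With the lead spread uniformly over a window and f = 10-40%:

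| Start of incapacity before death | Overstatement (points) |
|---|---|
| 0-3 months | 0 |
| 1-6 months | 0.1-0.5 |
| 3-12 months | about 1-5 |
| 6-18 months | about 1.5-8 |

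With f = 20-40%, the two longer windows lose 6-23% of the deaths within 24 months.

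**If deaths are recovered.** With full dates and inclusion in the analysis, survival returns to the true value and this bias is zero. Late exacerbations and hospitalizations are still not recovered.

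**Scale.** Protocol Table 2 gives 44.34% to 55.66% at n = 300 and 50%, a half-width of 5.66 points. Most settings above fall below that. The longest incapacity combined with the larger shares exceeds it.

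**The case against.** The strongest reply is that these patients are already covered. Protocol 9.3.2 defines withdrawal broadly enough to include a patient who is unable to go on taking part. Its list of reasons is open and includes the investigator's decision. It requires date, vital status and reason to be recorded for anyone removed or withdrawn. On that reading the 9.5 call applies. Section 9.3.2 also allows public sources for survival status where a patient refuses contact, and 9.10 promises efforts to reach patients lost to follow-up. Finally, the registry is descriptive and the curves are illustrative.

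Much of this stands. A reader might infer that the rule certainly overstates survival, or that these patients certainly miss the survival call. The documents support neither. Nor is the rule confined to the sickest: 9.4 gives temporary inability as its example, and short terminal incapacity often triggers no censoring.

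The reply does not close the gap:

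- No sentence links censoring under 9.4 to withdrawal under 9.3.2 or to the call in 9.5, so sites may differ.
- The call is described as a check of survival status at study end. A death learned then with a partial date falls under the SAP 6.6 exclusion.
- The SAP does not say whether a death learned after censoring counts.
- The dropout comparison in 9.10 describes such patients but corrects nothing.
- None of these routes restores non-fatal events, beyond one further assessment if possible.

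**Conclusion.** The contradiction within 9.4 is plain on the page, and the loss of later non-fatal events is the firmer consequence. Upward bias in survival is conditional. It arises if inability to attend outlasts a gap between visits, is related to prognosis, and the later deaths do not reach the analysis with full dates. The documents do not settle the last condition.

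The size runs from zero to about 8 points of 24-month survival across the assumed windows with 10-40% of deaths affected. It reaches about 14 only if half of all patients are unable to attend for a full year before death. The share, the duration and permanent incapacity are assumptions without a source in the documents. This should be fixed, because the gap is real and cheap to close, but it does not undermine the registry as a whole.

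**What to change.** - **Protocol 9.4:** replace the censoring sentence. Non-attendance makes only the measurements that need attendance missing. Vital status (with date and cause of death), hospitalizations, exacerbations and treatment continue to be recorded at each planned visit to month 24, by telephone or from the medical record. This also removes the conflict with the sentence that follows.
- **Protocol 9.5:** state that the survival contact covers patients who stop attending, and that it asks for the full date of death.
- **SAP 4 and 6.6:** state that non-attendance is not a reason for censoring when later vital status is known, and how deaths learned later enter the Kaplan-Meier curves.

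The cost is wording in both documents, the amendment approval described in Protocol 10.1, and some telephone calls or record checks by routes the protocol already uses. The downside is that event details taken by telephone are less complete than those taken at a clinic visit.
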